8.4.1.1. Reporting SAEs to Pfizer Safety

All SAEs occurring in a participant during the active collection period as described in [Section 8.4.1](#) are reported to Pfizer Safety on the Vaccine SAE Report Form or, if applicable, via PSSA, immediately upon awareness and under no circumstance should this exceed 24 hours, as indicated in [Appendix 2](#). The investigator will submit any updated SAE data to the sponsor within 24 hours of its being available.

8.4.1.2. Recording Nonserious AEs and SAEs on the CRF

All nonserious AEs and SAEs occurring in a participant during the active collection period, which begins after obtaining informed consent as described in [Section 8.4.1](#), will be recorded on the AE section of the CRF.

The investigator is to record on the CRF all directly observed, and all spontaneously reported AEs and SAEs reported by the participant.

As part of ongoing safety reviews conducted by the sponsor, any nonserious AE that is determined by the sponsor to be serious will be reported by the sponsor as an SAE. To assist in the determination of case seriousness, further information may be requested from the investigator to provide clarity and understanding of the event in the context of the clinical study.

If a participant begins a new therapy, the recording period for nonserious AEs ends at the time the new treatment is started; however, SAEs must continue to be recorded on the CRF during the above-indicated active collection period. A switch to a commercially available version of the study intervention is considered as a new therapy for the purposes of SAE reporting.

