Review reactogenicity e-diary data	X	X				E-diary data are transmitted daily to a Web-based portal for review by the investigator or delegate (preferably on a daily basis) during the 7-day e-diary follow-up period. Assess and manage any noncompliance.
Ask the participant to contact site staff in the event of any severe local reactions or systemic events in the 7-day e-diary follow-up period	X					If the participant does not call, site staff must contact the participant to determine whether an unscheduled reactogenicity visit is required.
Remind the participant to bring their e-diary/smartphone to the next study visit	X	X				
Collect stop dates for any symptoms marked as ongoing on the last day of the e-diary collection period in the CRF		X	X	X		

Table 2. Schedule of Activities

Visit Number	Visit 1	Visit 2	Visit 3	Visit 4	Unscheduled Reactogenicity Visit	Notes
Visit Description	Day 1 Vaccination	1-Week Follow-Up	1-Month Follow-Up	2-Month Follow-Up	Safety Assessment	
Visit Window (Days)		7 to 13 Days After Vaccination	28 to 35 Days After Vaccination	56 to 70 Days After Vaccination	N/A	Day relative to study intervention administration (Day 1)
Type of Visit						 : Clinic visit,  : Phone visit
Ensure all e-diary data have been transferred, collect provisioned e-diary, or assist participant with deleting the application, as appropriate			X			Do not deactivate the e-diary until all data are confirmed as having been transferred to the e-diary data management system.
Obtain details and record any AEs	X	X	X		X	See Section 8.4.2 .
Obtain details and record any AESIs	X	X	X	X	X	See Section 8.4.8 .
Obtain details and record any SAEs and NDCMCs	X	X	X	X	X	See Section 8.4.2 .
Measure minimum and maximum diameter of redness (if present) or swelling (if present)					X	
If present, assess the severity of necrosis or exfoliative dermatitis at the injection site					X	
If present, assess the severity of any injection site pain					X	
If present, assess the severity of any systemic event (fatigue, headache, nausea, vomiting, diarrhea, muscle pain, or joint pain)					X	

PFIZER CONFIDENTIAL

CT02-GSOP Clinical Protocol Template Phase 1 2 3 4 (14 April 2023)

Table 2. Schedule of Activities

Visit Number	Visit 1	Visit 2	Visit 3	Visit 4	Unscheduled Reactogenicity Visit	Notes
Visit Description	Day 1 Vaccination	1-Week Follow-Up	1-Month Follow-Up	2-Month Follow-Up	Safety Assessment	

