For all participants, AEs will be collected from informed consent through 1 month following study intervention administration. SAEs, NDCMCs, and AESIs will be collected from informed consent throughout study participation.

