8.4.1. Time Period and Frequency for Collecting AE and SAE Information

The time period for actively eliciting and collecting AEs and SAEs (“active collection period”) for each participant begins from the time the participant provides informed consent, which is obtained before the participant’s participation in the study (ie, before undergoing any study-related procedure and/or receiving study intervention), through and including Visit 4. At Visit 4 (2-month follow-up), the participant will be contacted by telephone to inquire about SAEs, including hospitalizations, NDCMCs, and AESIs since Visit 3.

- Nonserious AEs will be collected from informed consent through 1 month following study intervention administration (Visit 3).
- SAEs, including hospitalizations, NDCMCs, and AESIs will be collected from informed consent through the last study visit (Visit 4).

Follow-up by the investigator continues throughout the active collection period and until the AE or SAE or its sequelae resolve or stabilize at a level acceptable to the investigator.

When a clinically important AE remains ongoing at the end of the active collection period, follow-up by the investigator continues until the AE or SAE or its sequelae resolve or stabilize at a level acceptable to the investigator and Pfizer concurs with that assessment.

For participants who are screen failures, the active collection period ends when screen failure status is determined.

If the participant withdraws from the study and also withdraws consent for the collection of future information, the active collection period ends when consent is withdrawn.

If a participant permanently discontinues or temporarily discontinues the study because of an AE or SAE, the AE or SAE must be recorded on the CRF and the SAE reported via PSSA or using the Vaccine SAE Report Form.

Investigators are not obligated to actively seek information on AEs or SAEs after the participant has concluded study participation. However, if the investigator learns of any SAE, including a death, at any time after a participant has concluded study participation, and they consider the event to be reasonably related to the study intervention, the investigator must promptly report the SAE to Pfizer using the Vaccine SAE Report Form or, if applicable, via PSSA.

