8.10.3. Visit 3 (1-Month Follow-Up)

- Perform a clinical assessment and physical examination and record any findings in the source documents and, if the findings are clinically significant and meet the definition of an AE or SAE, record them on the CRF and according to the processes in [Section 8.4.1](#) to [Section 8.4.3](#).
- Obtain details of any nonstudy vaccinations and prohibited medications and treatments as described in [Section 6.9.1](#).
- Collect a blood sample of approximately 20 mL for antibody assessment.
- Review ongoing reactogenicity e-diary symptoms reported as present on the last day of the e-diary collection period and obtain stop dates. Record stop dates in the CRF if required. Any ongoing reactions must be assessed at the next contact.
- Ensure that all data have been transferred from the e-diary prior to deactivating the application.

- Collect the participant's e-diary provisioned device or assist the participant with removing the study application from their personal device.
- Record AEs, AESIs, NDCMCs, and SAEs as described in [Section 8.4](#) and [Section 10.2](#).
- If appropriate, discuss contraceptive use as described in [Section 10.3.1](#).
- Complete the source documents.
- The investigator or an authorized designee completes the CRFs.

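### Protocol 8.4.1.2 ends nonserious AE recording at an undefined new therapy, against the unconditional 1-month window in Protocol 8.4.1 and 4.1 and SAP 2.3

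*Protocol*

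**What the plan says.** Protocol 8.4.1.2 opens with a general rule, that "All nonserious AEs and SAEs occurring in a participant during the active collection period" are recorded on the AE section of the CRF. Later in the same section it adds a stop: "If a participant begins a new therapy, the recording period for nonserious AEs ends at the time the new treatment is started". SAE recording continues. The only guidance on the term is one example: "A switch to a commercially available version of the study intervention is considered as a new therapy for the purposes of SAE reporting".

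The other passages on AE collection do not state this stop:

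- Protocol 8.4.1: "Nonserious AEs will be collected from informed consent through 1 month following study intervention administration (Visit 3"). A separate bullet covers the other event types: "SAEs, including hospitalizations, NDCMCs, and AESIs will be collected from informed consent through the last study visit (Visit 4"). The section ends collection early only for screen failures and for withdrawal with withdrawn consent.
- Protocol 4.1: "For all participants, AEs will be collected from informed consent through 1 month following study intervention administration". SAP 2.3 has the same sentence.
- Protocol 1.3, Schedule of Activities: the row "Obtain details and record any AEs" is marked for Visits 1, 2 and 3 and the unscheduled visit, with no condition.
- Protocol 8.10.3, Visit 3: "Record AEs, AESIs, NDCMCs, and SAEs as described in" Section 8.4 and Section 10.2.
- Protocol 10.2.3: the recording table requires all nonserious AEs on the CRF.

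AEs within 1 month after vaccination are part of the primary safety estimand (Protocol Section 3; SAP 2.2.1.2.2). SAP 2.2.1.2.1 sets a treatment-policy strategy for safety, and SAP 6.1.3.1 includes all data collected after intercurrent events.

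**The concern.** A site that follows 8.4.1.2 literally may stop recording nonserious AEs before Visit 3, while the rest of the plan assumes they are recorded to Visit 3. The example does not resolve this. It is tied to SAE reporting, and SAE recording is what the clause leaves running.

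Treatment policy can include only events that reach the database. The SAP derives the AE endpoints as yes or no for each participant (SAP 3.1.2.2), so a participant whose only AE went unrecorded becomes a no, with no sign that data are missing. The tiered AE summaries could also be touched. A preferred term is Tier 2 if at least 4 participants in one group report it (SAP 3.3.1), and Tier 3 terms get no between-group confidence interval (SAP 6.3.1). A few lost reports could therefore change what is presented for a term.

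**Working it through.** The plan states no figure for this point, so there is none to reproduce. The check has three steps.

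**1. Can the texts be read together?** There are two readings of new therapy.

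- *Narrow: a product that replaces the study intervention.* The clause then has almost nothing to act on. The study is single-dose (Protocol 7.1), no RSV vaccine is approved in Korea (4.2.1) and nonstudy RSV vaccines are prohibited (6.9.1).
- *Broad: any newly started vaccine or medicine.* Protocol 6.9.2 permits nonlive or recombinant licensed vaccines from 14 days after vaccination (Day 15), and medication to treat vaccination symptoms throughout. The clause then operates inside the primary AE window.

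Nothing in 8.4.1.2 limits the sentence to the narrow reading. Under either reading it is at odds with 8.4.1, 4.1 and SAP 2.3, which carry no such exception.

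**2. Window lost per affected participant (broad reading).** Inputs: Visit 3 falls W = 28 to 35 days after vaccination (Schedule of Activities), and the start is at d = 14 days (Protocol 6.9.2). The share lost is (W − d)/W.

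- W = 28: (28 − 14)/28 = 14/28 = 50%
- W = 35: (35 − 14)/35 = 21/35 = 60%

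**3. Effect on the any-AE percentage.** An affected participant is missed only if the first AE comes after the start. With true 1-month any-AE rate p and a constant AE rate over time, the missed share among affected participants is (1 − p)^(d/W) − (1 − p). The documents do not give p, the share f of an arm affected, or the time pattern. All three are assumptions.

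| Assumed p | Missed, W = 28 | Missed, W = 35 | Clopper-Pearson 95% CI at n = 240 | Half-width |
|---|---|---|---|---|
| 5% | 2.47 points | 2.97 points | 12/240: 2.61% to 8.57% | 2.98 |
| 10% | 4.87 points | 5.87 points | 24/240: 6.51% to 14.51% | 4.00 |
| 20% | 9.44 points | 11.46 points | 48/240: 15.13% to 25.63% | 5.25 |

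The fall in the arm's any-AE percentage is f times the missed share:

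- f = 0: 0 points
- f = 5%, p = 10%: 0.05 × 4.87 = 0.24 to 0.05 × 5.87 = 0.29 points
- f = 10%, p = 20%, W = 35: 0.10 × 11.46 = 1.15 points, or 240 × 0.10 × 0.1146 = 2.75 participants in the RSVpreF arm

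**The case against.** The strongest reply is that 8.4.1.2 sits under 8.4.1 and may be a specific exception to it. The other passages are summaries: 4.1 and SAP 2.3 also omit the withdrawn-consent ending, the Schedule of Activities calls itself an overview, and the Visit 3 instruction refers back to Section 8.4, which contains the clause. The single example points to replacement of the study product, and the protocol uses other terms for nonstudy vaccines and concomitant medicines. Protocol 10.2.1 treats sequelae of drug interactions as AEs, and 8.4.3 asks for concomitant medications relevant to an event. A broad stop sits badly with both. The assumed effect is small, the study tests no hypothesis, and SAP 6.1.3.1 speaks only of data that were collected.

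Much of this stands as a limit on the size of the problem. The narrow reading may well be the intended one, and the unconditional instructions elsewhere make systematic early stopping less likely. It does not remove the conflict. If the clause is a working exception, it shortens the primary AE window, and the two all-participant statements are not true as written. If it is inert, it contradicts those statements for no purpose. Sections 10.2.1 and 8.4.3 are further text that a stop would conflict with.

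**Conclusion.** The concern holds. Protocol 8.4.1.2 is wrong as written: followed literally, it leaves a primary endpoint incompletely captured. Confidence is high that the passages conflict. The amount lost in practice is not established.

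On the narrow reading the loss is nil. On the broad reading, under the assumed p, f and constant rate, the any-AE percentage in an arm falls by at most 1.15 points, well inside the interval half-width. The documents give no therapy-start rates, so neither the size nor the direction of any between-group effect can be stated.

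The reach is also limited:

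- SAEs and e-diary reactogenicity are unaffected.
- AESIs and NDCMCs have their own rule through Visit 4 and are not claimed as lost.
- A participant with an earlier recorded AE still counts in the any-AE endpoint.
- Stops tied to a nonstudy vaccine or prohibited treatment could be checked on the CRF (Protocol 6.9.3). Stops tied to a permitted medicine could not be checked from that list.

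**What to change.** Delete the new-therapy stop and its example from Protocol 8.4.1.2. Replace them with one statement that the 8.4.1 windows apply to every vaccinated participant regardless of later therapy: nonserious AEs through Visit 3; SAEs, NDCMCs and AESIs through Visit 4. The existing ending for withdrawn consent stays. The SAP text needs no change.

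If sites are active, send a clarification letter and ask whether AE recording was ended early for any participant on this ground, because unrecorded events become harder to recover with time.

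The cost is a wording change or a site letter, and possibly a few more nonserious AEs to record.

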8.4.2. Method of Detecting AEs and SAEs

The method of recording, evaluating, and assessing causality of AEs and SAEs and the procedures for completing and transmitting SAE reports are provided in [Appendix 2](#).

Care will be taken not to introduce bias when detecting AEs and/or SAEs. Open-ended and nonleading verbal questioning of the participant is the preferred method to inquire about AE occurrences.

8.4.3. Follow-Up of AEs and SAEs

After the initial AE or SAE report, the investigator is required to proactively follow each participant at subsequent visits/contacts. For each event, the investigator must pursue and obtain adequate information until resolution, stabilization, the event is otherwise explained, or the participant is lost to follow-up (as defined in [Section 7.3](#)).

In general, follow-up information will include a description of the event in sufficient detail to allow for a complete medical assessment of the case and independent determination of possible causality. Any information relevant to the event, such as concomitant medications and illnesses, must be provided. In the case of a participant death, a summary of available autopsy findings must be submitted as soon as possible to Pfizer Safety.

Further information on follow-up procedures is provided in [Appendix 2](#).

8.4.4. Regulatory Reporting Requirements for SAEs

Prompt notification by the investigator to the sponsor of an SAE is essential so that legal obligations and ethical responsibilities toward the safety of participants and the safety of a study intervention under clinical investigation are met.

The sponsor has a legal responsibility to notify both the local regulatory authority and other regulatory agencies about the safety of a study intervention under clinical investigation. The sponsor will comply with country-specific regulatory requirements relating to safety reporting to the regulatory authority, IRBs/ECs, and investigators.

Investigator safety reports must be prepared for SUSARs according to local regulatory requirements and sponsor policy and forwarded to investigators as necessary.

An investigator who receives SUSARs or other specific safety information (eg, summary or listing of SAEs) from the sponsor will review and then file it along with the SRSD(s) for the study and will notify the IRB/EC, if appropriate according to local requirements.

8.4.5. Environmental Exposure, Exposure During Pregnancy or Breastfeeding, and Occupational Exposure

Environmental exposure occurs when a person not enrolled in the study as a participant receives unplanned direct contact with or exposure to the study intervention. Such exposure may or may not lead to the occurrence of an AE or SAE. Persons at risk for environmental exposure include healthcare providers, family members, and others who may be exposed. An environmental exposure may include EDP, EDB, and occupational exposure.

Any such exposures to the study intervention under study are reportable to Pfizer Safety within 24 hours of investigator awareness.

8.4.5.1. Exposure During Pregnancy

An EDP occurs if:

- A male participant who is receiving or has discontinued the study intervention inseminates a female partner.
- A female participant is found to be pregnant while receiving or after discontinuing the study intervention.
- A female nonparticipant is found to be pregnant while being exposed or having been exposed to the study intervention because of environmental exposure. Below are examples of environmental EDP:
 - A female family member or healthcare provider reports that she is pregnant after having been exposed to the study intervention by needlestick injury, inhalation, or skin contact.
 - A male family member or healthcare provider who has been exposed to the study intervention by needlestick injury, inhalation, or skin contact then inseminates his female partner prior to or around the time of conception.

The investigator must report the EDP to Pfizer Safety within 24 hours of the investigator's awareness, irrespective of whether an SAE has occurred. The initial information submitted should include the anticipated date of delivery (see below for information related to termination of pregnancy).

- If an EDP occurs in a participant/participant's partner, the investigator must report this information to Pfizer Safety via PSSA or using the Vaccine SAE Report Form and an EDP Supplemental Form, regardless of whether an SAE has occurred. Details of the pregnancy will be collected after the start of study intervention and until the end of study.
- If an EDP occurs in the setting of environmental exposure, the investigator must report this information to Pfizer Safety using the Vaccine SAE Report Form and an EDP Supplemental Form. Since the exposure information does not pertain to the participant enrolled in the study, the information is not recorded on a CRF; however, a copy of the completed report is maintained in the investigator site file.

Follow-up is conducted to obtain general information on the pregnancy and its outcome for all EDP reports with an unknown outcome. The investigator will follow the pregnancy until completion (or until pregnancy termination) and notify Pfizer Safety of the outcome as a follow-up to the initial report. In the case of a live birth, the structural integrity of the neonate can be assessed at the time of birth. In the event of a termination, the reason(s) for termination should be specified and, if clinically possible, the structural integrity of the terminated fetus should be assessed by gross visual inspection (unless preprocedure test findings are conclusive for a congenital anomaly and the findings are reported).

Abnormal pregnancy outcomes are considered SAEs. If the outcome of the pregnancy meets the criteria for an SAE (ie, ectopic pregnancy, spontaneous abortion, intrauterine fetal demise, neonatal death, or congenital anomaly in a live-born baby, or a terminated fetus), the investigator should follow the procedures for reporting SAEs. Additional information about pregnancy outcomes that are reported to Pfizer Safety as SAEs follows:

- Spontaneous abortion, including miscarriage and missed abortion, should be reported as an SAE;
- Neonatal deaths that occur within 1 month of birth should be reported, without regard to causality, as SAEs. In addition, infant deaths after 1 month should be reported as SAEs when the investigator assesses the infant death as related or possibly related to exposure to the study intervention.

Additional information regarding the EDP may be requested by the sponsor. Further follow-up of birth outcomes will be handled on a case-by-case basis (eg, follow-up on preterm infants to identify developmental delays).

In the case of paternal exposure, the investigator will provide the participant with the Pregnant Partner Release of Information Form to deliver to his partner. The investigator must document in the source documents that the participant was given the Pregnant Partner Release of Information Form to provide to his partner.

8.4.5.2. Exposure During Breastfeeding

An EDB occurs if:

- A female nonparticipant is found to be breastfeeding while being exposed or having been exposed to the study intervention (ie, environmental exposure). An example of environmental EDB is a female family member or healthcare provider who reports that she is breastfeeding after having been exposed to the study intervention by needlestick injury, inhalation, or skin contact.

The investigator must report the EDB to Pfizer Safety within 24 hours of the investigator's awareness, irrespective of whether an SAE has occurred. The information must be reported using the Vaccine SAE Report Form or, if applicable, via PSSA. When EDB occurs in the setting of environmental exposure, the exposure information does not pertain to the participant enrolled in the study, so the information is not recorded on a CRF. However, a copy of the completed report is maintained in the investigator site file.

An EDB report is not created when a Pfizer drug specifically approved for use in breastfeeding women (eg, vitamins) is administered in accordance with authorized use. However, if the infant experiences an SAE associated with such a drug, the SAE is reported together with the EDB.

